4 STUDY OVERVIEW

4.1 Study Design

This is a randomized, double-blind, vehicle-controlled, parallel group dose-response study evaluating the safety and effectiveness of 2 concentrations of NFX-179 Gel in subjects with cutaneous neurofibromas (cNF).

At Visit 1, the investigator will identify 10 Target cNFs that fulfill the enrollment criteria for treatment. The Target cNFs must be located on the subject's face, anterior trunk, or upper extremities. Preferably 2 Target cNFs are located on the face and 8 Target cNFs are located on the anterior trunk or upper extremities. Alternatively, at least 1 Target cNF is located on the face, in which case 9 Target cNFs must be located on the anterior trunk or upper extremities.

At Visit 2 (Day 1, Week 0) eligible subjects will be randomized and will begin the 182 day/26-week QD treatment period. The subject will apply the assigned study medication to the Target cNFs QD during the treatment period. The subject may have cNFs other than the Target cNFs but only the Target cNFs will be treated and evaluated.

Subjects will be seen at Visits 3-7 (Days 8, 29, 57, 85 and 141/Weeks 1, 4, 8, 12 and 20) for

follow-up visits during the treatment period.

At Visit 8 (Day 183/Week 26) subjects will be seen for the last treatment period visit and subjects will begin a 4-week no treatment follow-up period

At Visit 9 (Day 211/Week 30) subjects will be seen for an end of study visit.

No topical therapies for cNF other than the study medication may be used on any of the Target cNFs for the duration of the study.

As part of the clinical development program for NFX-179 Gel a subset of randomized subjects who complete this study (approximately 20%) may be invited to participate in an administratively separate exit interview study to learn about their experience in the study and to assist with their perception of clinically meaningful change in NF1.

A Coordinating Investigator, [REDACTED], is designated by the Sponsor. The Coordinating Investigator is responsible for the overall conduct of the study and signing the Clinical Study Report on behalf of the participating site investigators upon study conclusion.

4.2 Dose Selection Rationale

The selection of doses, dosing interval and duration considered the results of the nonclinical pharmacology, pharmacokinetic and toxicology studies, which are presented in the Investigator's Brochure (IB).

The QD topical application frequency at the proposed concentrations is expected to result in continuous exposure at efficacious levels in a safe range.

4.3 End of Study Definition

The end of the study is defined as the date of the last visit of the last subject in the study globally.

If the Medical Monitor or designee, study monitor, or appropriate regulatory officials indicate that the study should be halted or that a study site should be terminated, this action may be taken after appropriate consultation between NFlection and the appropriate parties. NFlection has the right to terminate this study at any time for any reason.

Conditions that may warrant termination of the study include, but are not limited to:

- The discovery of an unexpected, serious, or unacceptable risk to the subjects enrolled in the study.
- A decision by NFlection to suspend or discontinue testing, evaluation, or development of the product.

4.4 Study Duration

The duration of study participation for each subject is anticipated to be a maximum of 242 days. Including an up to 28-day screening period, a 182-day treatment period and a 28-day no-treatment follow-up period. The last study visit has a window of ± 4 days.

The duration of the study from first subject first visit to last subject last visit is planned to be approximately 86 weeks. The study end date is the date of the last subject's last visit.

5 STUDY POPULATION

This study will enroll male and female subjects at least 18 years of age, with a clinical diagnosis of NF1.

5.1 Number of subjects

Approximately 168 subjects will be randomized to 1 of the 3 study medication treatment groups at approximately 27 United States (US) investigational centers with the goal of at least 150 randomized subjects completing the study.

5.2 Study Entry Criteria

5.2.1 Inclusion Criteria

To be eligible to participate in this study at Visit 1, the subject must fulfill all the following criteria:

1. Subject is at least 18 years of age
2. Subject must provide written informed consent prior to any study procedures

3. Subject must have a clinical diagnosis of NF1
4. Subject has 10 clinically diagnosed Target cNFs with preferably 2 Target cNFs located on the face and 8 Target cNFs located on the anterior trunk or upper extremities. Alternatively, at least 1 Target cNF is located on the face, in which case 9 Target cNFs must be located on the anterior trunk or upper extremities. Each Target cNF must meet the following criteria:
 - Has, in the investigator's opinion, a clinically typical appearance
 - Is not within 1 cm of the orbital rim
 - Is not covered with hair that might, in the investigator's opinion, interfere with obtaining photographs or impair evaluation of the cNF
 - Has a Physician's Tumor Assessment grade ≥ 2
 - Is dome shaped
 - Is not pedunculated
 - Is a discrete cNF surrounded by sufficient non-affected skin that, in the investigator's opinion:
 - i. The dimensions can be measured
 - ii. The perimeter can be outlined in the study photographs
 - Is not irritated (*e.g.*, bleeding, inflamed)
 - Is not in an area subject to repeated trauma (*e.g.*, area that is shaved, on the beltline, under a bra strap, etc.)
 - Does not have an active cutaneous infection
 - Target cNFs on the face must have the following tumor dimensions:
 - i. Has a length that is $\geq 5\text{mm}$ and $\leq 14\text{mm}$
 - ii. Has a width that is $\geq 5\text{mm}$ and $\leq 14\text{mm}$
 - iii. Has a height that is $\geq 2\text{mm}$.
 - Target cNFs on the anterior trunk or upper extremities must have the following tumor dimensions:
 - i. Has a length that is $\geq 7\text{mm}$ and $\leq 14\text{mm}$
 - ii. Has a width that is $\geq 5\text{mm}$ and $\leq 14\text{mm}$
 - iii. Has a height that is $\geq 2\text{mm}$
5. Subject agrees to minimize exposure of Target cNFs to sunlight and to use her/his routine sunscreen if exposure cannot be avoided
6. Subject agrees NOT to use tanning beds
7. Subject is willing to forego treatment of each Target cNF, except protocol specified therapy, during the study
8. Female subjects who are women of childbearing potential must have a negative urine pregnancy test result and be willing to use a protocol approved, contraceptive method for the duration of the study
9. Subject is willing and able to follow all study instructions and to attend all study visits.

5.2.2 Exclusion Criteria

A subject who meets any of the following criteria at Visit 1 (except where noted at Visit 2) will be excluded from participation in this study:

1. Subject has used any of the following topical therapies within the specified period prior to Visit 2 on or in proximity to any Target cNF that, in the investigator's opinion, impairs evaluation of any the cNFs or which exposes the subject to an unacceptable risk by study participation:
 - Corticosteroids; 30 days
 - Prescription retinoids (*e.g.*, tazarotene, tretinoin, adapalene); 30 days
 - > 5% of an alpha-hydroxy acid (*e.g.*, glycolic acid, lactic acid); 30 days
 - Fluorouracil; 30 days
 - Imiquimod; 30 days
 - LASER, light (*e.g.*, intense pulsed light [IPL], photo-dynamic therapy [PDT]) or other energy-based therapy; 180 days
 - MEK inhibitor or BRAF inhibitor; ever.
2. The subject has used any of the following systemic medications therapies within the specified period prior to Visit 2:
 - Retinoids (*e.g.*, etretinate, isotretinoin); 90 days
 - MEK inhibitors; 180 days
 - BRAF inhibitors; 180 days
3. Subject has a history of hypersensitivity to any of the ingredients in the study medications
4. Subject has any known intercurrent illness or physical condition that would, in the investigator's opinion, impair evaluation of a Target cNF or which exposes the subject to an unacceptable risk by study participation
5. Subject has, in the investigator's opinion, clinically relevant history of liver disease, including viral hepatitis, current alcohol abuse, or cirrhosis
6. Subject has a history of metastatic disease, or active cancer (excluding non-melanoma skin cancer, Stage I cervical cancer, ductal carcinoma *in situ* of the breast, or Stage 0 chronic lymphocytic lymphoma) within the previous 5 years
7. Subject has any condition (*e.g.*, other skin conditions or diseases, metabolic dysfunction, physical examination findings, clinical laboratory findings) or situation (*e.g.*, vacation, scheduled surgery) that would, in the investigator's opinion, impair evaluation of a Target cNF or which exposes the subject to an unacceptable risk by study participation
8. Subject has participated in an investigational drug trial in which administration of an investigational study medication occurred within the previous 30 days.

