In the GLP 13-week oral toxicology/TK study in the rat, NFX-179 was well tolerated at dose levels of up to [REDACTED] mg/kg/day for 13 weeks, with toxicity limited to reductions in white blood cell counts in males at [REDACTED] mg/kg/day and red cell counts in females given [REDACTED] mg/kg/day, which were reversible following a 4-week treatment-free period. These findings correlated with increased incidence of adipocytes in the bone marrow and extramedullary haematopoiesis in the spleen at the end of the dosing period; however, as the peripheral blood changes were reversible, these microscopic findings were considered not to be adverse. The NOAEL was considered to be [REDACTED] mg/kg/day, equivalent to a C_{max} after 13 weeks of [REDACTED] or [REDACTED] ng/mL, and an AUC₀₋₂₄ of [REDACTED] or [REDACTED] ng.h/mL, in males and females, respectively.

NFX-179 was not mutagenic, clastogenic or aneugenic when evaluated in both in vitro and in vivo genetic toxicity tests. NFX-179 Gel was found to have no potential for skin sensitization, and there was no potential for eye irritation. NFX-179 showed high levels of light absorbance in the UV/Vis range, indicating that it has the potential to be phototoxic and photosensitizing.

Full details of the nonclinical studies for NFX-179 Gel are presented in the Investigator's Brochure.

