5.6.4 Subject randomization

At Visit 2, the investigator will determine the subject's eligibility for randomization to study medication. To be eligible for randomization the subject must:

- Have a PTA ≥ 2 for all Target cNFs
- Have clinical laboratory test results for all measured analytes at Visit 1 and all results are either within the range of normal for the laboratory or, any abnormal results, are defined as Not Clinically Relevant (NCR) by the investigator.
- Have, if a Woman of Childbearing Potential (WOCBP), a negative urine pregnancy test result at Visit 2.
- Have NOT used any topical or system therapies within the specified period prior to Visit 2 per the exclusion criteria

The investigator or designee will assign study medication to eligible subjects by selecting the

Subject Kits in chronological sequence in ascending numerical order starting with the lowest available Subject Kit number. The investigator will not omit or reuse any Subject Kit number.

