Subjects should not apply the study medication within 6 hours prior to a study visit, except on Visit 4 when the subject should apply study medication 4 (\pm 2 hours) prior to the scheduled appointment time. Record the study medication application time on the day of Visit 4.

If during the treatment phase a Target cNF clears (*i.e.*, PTA grade of 0) instruct the subject to continue QD application to the area of the cNF for the remainder of the treatment period.

After completing a study medication application, a subject should not:

- Wash or submerge any Target cNF for at least 6 hours
- Apply any topical products (*e.g.*, cosmetics, emollient/moisturizer, sunscreens) to any Target cNF for at least 6 hours.

At Visits 3-7 review the application technique with the subject to ensure they are performing the application properly, are using an appropriate amount of study medication and are applying the study medication to the correct cNFs.

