At Visit 1 the investigator will identify 10 clinically diagnosed Target cNFs. Preferably 2 Target cNFs are located on the face and 8 Target cNFs are located on the anterior trunk or upper extremities. Alternatively, at least 1 Target cNF is located on the face, in which case 9 Target cNFs must be located on the anterior trunk or upper extremities.

For this study, the face, anterior trunk, and upper extremities are defined as follows:

- Face:
 - Vertically from the mandibular ridge to the hairline (for subjects with a receding hair the hairline is defined by a vertical line drawn coronally from tragus to tragus)
 - Horizontally from tragus to tragus, excluding the eyelids, eyebrows, and areas within 1 cm of the orbital rim.
- Anterior trunk:
 - The front of the torso down to the beltline, excluding the neck
- Upper extremities:
 - Arms from the shoulders to the wrist, (excluding the hands).

[figure not shown]
At Visit 1 each of the 10 clinically diagnosed Target cNFs must meet the following criteria for the subject to be enrolled:

- Has, in the investigator's opinion, a clinically typical appearance
- Is not within 1 cm of the orbital rim

- Is not covered with hair that might, in the investigator's opinion, interfere with obtaining photographs or impair evaluation of the cNF
- Has a PTA grade ≥ 2
- Is dome shaped
- Is not pedunculated
- Is a discrete cNF surrounded by sufficient non-affected skin that, in the investigator's opinion:
 - i. The dimensions can be measured
 - ii. The perimeter can be outlined in the study photographs
- Is not irritated (*e.g.*, bleeding, inflamed)
- Is not in an area subject to repeated trauma (*e.g.*, on the beltline, under a bra strap, etc.)
- Does not have an active cutaneous infection
- Target cNFs on the anterior trunk or upper extremities must have the following tumor dimensions:
 - i. Has a length that is $\geq 7\text{mm}$ and $\leq 14\text{mm}$
 - ii. Has a width that is $\geq 5\text{mm}$ and $\leq 14\text{mm}$
 - iii. Has a height that is $\geq 2\text{mm}$.
- Target cNFs on the face must have the following tumor dimensions:
 - i. Has a length that is $\geq 5\text{mm}$ and $\leq 14\text{mm}$
 - ii. Has a width that is $\geq 5\text{mm}$ and $\leq 14\text{mm}$
 - iii. Has a height that is $\geq 2\text{mm}$

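### The eligibility criteria are silent on breast-feeding, so a nursing woman can enter and contact exposure of her infant to the gel is possible under the protocol as written

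*Combined protocol and SAP*

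**What the plan says.** Section 5.2.2 opens with "A subject who meets any of the following criteria at Visit 1 (except where noted at Visit 2) will be excluded from participation" and lists eight criteria. They concern prior topical and systemic therapies, hypersensitivity, intercurrent illness, liver disease, cancer history, other conditions or situations, and recent trial participation. Criteria 4 and 7 are left to the investigator's opinion and apply to something that would "impair evaluation of a Target cNF or which exposes the subject to an unacceptable risk by study participation".

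The only reproductive entry criterion is in 5.2.1: "Female subjects who are women of childbearing potential must have a negative urine pregnancy test result". The same criterion asks these women to agree to an approved form of contraception while they are in the study. Section 5.6.4 repeats the test before randomization: "Have, if a Woman of Childbearing Potential (WOCBP), a negative urine pregnancy test result at Visit 2".

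Section 6.3 defines the anterior trunk as "The front of the torso down to the beltline, excluding the neck". Among the things 5.6.8 tells subjects not to do after applying the gel is "Wash or submerge any Target cNF for at least 6 hours".

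**The concern.** The protocol takes care over exposure in pregnancy. Urine tests are scheduled at eight visits (1, 2, and 4 to 9). Contraception runs to 30 days after the last application, pregnancies are reported up to 6 months after it, and infants are followed for at least six weeks after exposure in pregnancy. It makes no provision for a child who is already born and being nursed.

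That child could meet the drug in two ways: by contact with treated skin, and through milk. An infant cannot consent and has nothing to gain from the exposure. The safety procedures are written around enrolled subjects, so no scheduled assessment would look for a problem in the infant. With about 27 centers and no written rule, sites may also decide differently whether a nursing woman may enter.

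**Working it through.** No arithmetic decides this point, and the plan gives no figure to reproduce. The check is whether any provision, alone or combined with others, keeps a nursing woman out or deals with the infant.

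**1. Is breast-feeding addressed anywhere?** The places read were the synopsis criteria, 5.2.1, 5.2.2, 5.6.4, the application and subject instructions (5.6.8, 5.9), 7.1.7 and 8.6 with its subsections. None mentions breast-feeding, lactation or nursing. The word breast occurs only in the cancer-history exclusion. The entry criteria are shown in full, so this is not an effect of redaction.

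**2. Does the reproductive criterion exclude nursing women indirectly?** No. It asks for a negative pregnancy test and an approved contraceptive method. The methods in 8.6.2 include abstinence, intrauterine devices and progestogen-only hormones, and a woman who is nursing can satisfy both parts. Because entry needs negative tests at Visits 1 and 2, and a later positive test leads to withdrawal (7.1.7), the women chiefly concerned are those already nursing at entry.

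**3. Do the discretionary criteria close the gap?** Criteria 4 and 7 permit exclusion for impaired tumor evaluation or for unacceptable risk to the subject. Neither names risk to anyone else, and neither requires an investigator to ask about nursing.

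**4. Can treated skin be skin that an infant touches?** Eight or nine of the ten Target tumors are on the anterior trunk or upper extremities (5.2.1). The trunk definition removes the neck but not the breast. Tumors in areas of repeated trauma are excluded, with the position under a bra strap as one example. A breast site is therefore allowed but never required, since all non-facial targets could be on the abdomen or arms.

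**5. How much gel, and for how long?** Each target is at most 14 mm by 14 mm at entry. Ten targets therefore have a combined footprint of at most 10 × 1.4 cm × 1.4 cm = 19.6 cm², taking each as a full square, which overstates it. The gel is a thin layer rubbed in until none is visible, with hands washed before and after (5.6.8). Application is once daily for 182 days, and leaving the site unwashed for at least 6 hours is an instruction. Together these permit contact; they do not measure it.

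**6. What do the documents say about hazard?** In the 13-week oral rat study, 2.2.1 reports "toxicity limited to reductions in white blood cell counts in males at" a dose level that is blacked out, and lower red cell counts in females. The same paragraph calls the drug well tolerated and says that these changes reversed over a 4-week treatment-free period. Systemic exposure after topical use in minipigs was very low. The 28-day study in 48 subjects (2.2.2) had no treatment-related adverse events. Nothing is given on transfer into milk, transfer from treated skin, or any infant dose.

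**7. Does anything else cover the infant?** Section 5.9 tells subjects to keep the product from children, which concerns the tube and not treated skin. The infant follow-up in 8.6.2 arises only from exposure in pregnancy.

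**The case against.** The strongest reply is that the gap may have no practical consequence. The footprint is small, the gel is rubbed in, topical absorption appears low, and a nursing woman with a target on the breast may never present. Investigators have wide discretion under criterion 7, may remove a subject under 5.4, and might judge skin in repeated contact with a nursing infant to be an area of repeated trauma. Section 8 asks them to alert the sponsor to anything unusual. The consent form and the Investigator's Brochure, which are not available here, may carry lactation advice.

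Much of this stands as a limit on the point, and it rules out several stronger readings that a reader might infer:

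- *Gel may be placed anywhere on the front of the torso.* It may not: the neck and areas of repeated trauma are excluded.
- *Several of the 168 subjects will be affected.* The documents give no basis for any count, and zero is compatible with them.
- *Each such infant would be exposed daily for 182 days.* That is a worst case. It needs a target where the infant makes contact, nursing throughout, and contact each day while gel remains.
- *The rat findings show a danger to the infant.* They come from oral dosing at redacted doses and were reversible. Nothing links those doses to what an infant could receive.
- *Subjects are not warned.* That cannot be known without the consent form.

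The reply does not remove the gap. Discretion framed around the subject's own risk is not a rule about an infant. Low systemic absorption bears on transfer through milk and does not address direct contact. A warning in the consent form would not be an eligibility criterion.

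**Conclusion.** The gap is real and its size is unknown. Followed exactly, the protocol would admit a nursing woman and have her apply a MEK inhibitor gel for 182 days to sites that can include the breast, without any provision for the infant. This is a precautionary omission in eligibility with a possible safety consequence. It has no bearing on the endpoints or the analysis, and it is not an internal contradiction.

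The conclusion rests on the protocol text alone. It assumes that no document outside it sets a binding rule on breast-feeding. It makes no assumption about how many subjects are nursing or how much drug an infant would receive, and no claim that harm would follow. It should be corrected because the remedy is cheap and the person at risk is not a participant.

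**What to change.** Add a breast-feeding criterion to 5.2.2, for example excluding a subject who is breast-feeding or intends to breast-feed during the study. Mirror it in the synopsis criteria and in the Visit 2 check in 5.6.4. The sponsor should confirm that the wording agrees with the Investigator's Brochure and the consent form. If the sponsor has grounds for admitting nursing women, the protocol should state that position and the reasons for it.

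The cost is one line in an amendment and one eligibility question. The downside is that a very small number of otherwise eligible women could not enter.

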5.3 Subject identifier (SI)

At Visit 1 (Screening) the investigator or designee will assign a unique four-digit subject identifier (SI) to each subject.

The SI format will be NN-NN where the first 2 digits are the investigational center site number (using leading zeroes as appropriate) assigned by NFlection. The final 2 digits are the subject

number and must be assigned in ascending numerical order, without omitting or repeating any number, starting with 01 at each investigational center. For example, the SI for the second subject that signs an informed consent at site number 14 would be 14-02.

The subject will be identified using the SI in all study documentation for the duration of the study.

